## Clinical Research Protocol

Title	Clinical Study and Molecular Mechanism of Xuesaitong Soft Capsule in the Treatment of Acute Coronary Syndrome After Percutaneous Coronary Intervention
Version Number	2024XLA098-2
Responsible Institution	Xiyuan Hospital of China Academy of Chinese Medical Sciences
Target Population	Patients with Acute Coronary Syndrome (ACS) after Percutaneous Target Population Coronary Intervention (PCI), both male and female, aged between 18 and 80 years.
Objective	To interpret the microcosmic manifestations of ACS development using multi-omics technologies, explore key biomarkers and the correlation Objective between disease and syndrome, and elucidate the macro and microcosmic manifestations and biological basis of Xuesaitong soft capsule in the treatment of ACS from multiple perspectives.
Study Design	Single-center, open-label, exploratory clinical study.
Sample Size	50 ACS patients post-PCI in an open-label group.
Study Duration	From October 13, 2024, to December 1, 2026.
Inclusion Criteria	
(1) Patients diagnosed with acute ST-segment elevation myocardial infarction, acute non-ST-segment elevation myocardial infarction, or unstable angina according to Western medical standards. Inclusion Criteria.
 
(2) Within 4 weeks post-PCI.
 
(3) Aged between 18 and 80 years, both male and female.
 
(4) Voluntarily participating in the clinical trial, having signed the informed consent form.

Exclusion Criteria	
 
(1) Uncontrolled hypertension after medication (systolic BP > 180mmHg or diastolic BP > 110mmHg).
 
(2) Increased bleeding risk: history of hemorrhagic stroke; intracranial aneurysm; major trauma or surgery within the past month (including Exclusion Criteria bypass surgery); active bleeding disorders.
 
(3) History of gastrointestinal ulcers or significant gastrointestinal bleeding.
 
(4) Severe organic heart disease, such as LVEF < 35% or NYHA/Killip heart function grade IV.
 
(5) History of malignant arrhythmias within the past year (arrhythmias affecting hemodynamics requiring medication or electrical cardioversion, or requiring CPR), congenital heart disease, or malignant tumors.
 
(6) Severe liver or kidney dysfunction: ALT or AST <math>\geq 3 \times \text{ULN}</math>, TBIL <math>\geq 2 \times \text{ULN}</math>, or creatinine clearance <math>< 30 \text{ ml/min}</math>.
 
(7) Pregnant or lactating women.
 
(8) Recent blood donation or significant blood loss within the past 3 months (<math>\geq 400 \text{ ml}</math>).
 
(9) History of alcohol abuse (<math>\geq 28</math> standard units/week for males, <math>\geq 21</math> standard units/week for females) or frequent alcohol consumption in the past 6 months (<math>\geq 14</math> standard units/week).
 
(10) History of drug abuse or dependence within the past year. Participation in other clinical trials and taking trial drugs within the past 3 months.
 
(11) Allergy or intolerance to aspirin or P2Y12 receptor inhibitors.
 
(12) Allergy to any components of the trial drug.
 
(13) Other conditions deemed inappropriate for participation by the investigator.
 

--------------------	---

Medication Information	
Trial Drug: Xuesaitong Soft Capsule.
 
Main Component: Panax Notoginseng Saponins.
 
Dosage Form: Capsule.
 
Dosage and Administration: Orally after meals, 0.33g per capsule, 2 capsules per dose, twice daily.
 
Storage Conditions: Room temperature, cool, dry place.

Medication Regimen	
Conventional Western medical treatment (oral medication and standard PCI) combined with Xuesaitong soft capsule, 0.33g per capsule, 2 capsules per dose, twice daily for 4 weeks.

Study Procedure	
Participants who meet the diagnostic criteria, inclusion, and exclusion criteria, and have signed the informed consent form will be included in the study. The open-label study period is 4 weeks, including 2 visits: Visit 1 (-1D to 0D) and Visit 2 (4w ± 3d), with no follow-up period.

Evaluation Criteria	
(1) General Information: Demographic data, physical examination, medical history, allergy history, smoking and alcohol history, concomitant medications.
 
(2) Multi-omics Analysis: Including platelet transcriptomics, metabolomics, proteomics, microbiomics.
 
(3) Platelet Function: platelet granule markers (PF4 and <math>\beta</math>-TG), surface activation markers (P-selectin/CD62P, GPIIb/IIIa complex/CD41/CD61), platelet-leukocyte aggregation (CD41 and CD15).
 
(4) Safety Indicators: Routine blood, urine, and stool tests (including occult blood), liver and kidney function tests, ECG, coagulation function, and adverse event recording.

Statistical Analysis Plan	
1. Analysis Data Sets
 
1.1 Full Analysis Set (FAS): Defined according to the ITT principle, including all enrolled participants who received at least one treatment.

1.2 Per-Protocol Set (PPS): Includes participants who met inclusion criteria, completed treatment and follow-up, had medication compliance between 80-120%, did not use concomitant medications affecting efficacy evaluation, had complete main outcome data, and no major protocol violations.

1.3 Safety Set (SS): Includes all enrolled participants who received at least one treatment. Baseline data analysis will be conducted separately for FAS and PPS. Efficacy indicators will be analyzed for both FAS and PPS. Safety and adverse events will be analyzed for SS.

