## 2. Statistical Method Description

2.1 Enrollment Analysis: List the number of enrolled and completed cases, and determine the analysis data sets (PPS, SS).

2.2 Demographic and Baseline Analysis: Descriptive statistics for demographic data and other baseline characteristics: Continuous variables: Calculate the number, mean, standard deviation, median, minimum, and maximum values. Categorical and ordinal data: Calculate frequencies and proportions. Inferential statistical results (P-values) will be listed as descriptive results. Age factors should be considered in data analysis, and data should be stratified or grouped by different age groups.

2.3 Efficacy Analysis: Primary Efficacy Indicators: Evaluate treatment effects through multi-omics analysis and platelet function indicators. Use descriptive and inferential statistical methods such as t-tests, chi-square tests, and Cox regression analysis to compare pre- and post-treatment differences. Secondary Efficacy Indicators: Include safety indicators and adverse event records. Use descriptive statistical methods such as frequency analysis and percentage calculations to describe the incidence and severity of adverse events.

	
2.4 Safety Analysis: Number and rate of laboratory indicators or physical examination abnormalities after treatment. List abnormal laboratory indicators, abnormal physical examination cases, and clinical interpretations.
 
2.5 Laboratory Data: Analyze changes in laboratory test results before and after treatment using paired t-tests or Wilcoxon signed-rank tests.
 
2.6 Adverse Events: Describe the types, frequencies, and severities of adverse events using chi-square tests or Fisher's exact tests for comparisons.
 
2.7 Multiple Comparison Adjustments: For multivariable statistical analyses, use Bonferroni correction or Holm-Bonferroni method to adjust significance levels and control type I error rates.
 
2.8 Critical Assumption Verification: Certain statistical methods require critical assumptions such as normality and homogeneity of variance. Verification methods include: Normality Test: Shapiro-Wilk test or Kolmogorov-Smirnov test. Homogeneity of Variance Test: Levene's test or Bartlett's test. This statistical analysis plan ensures the scientific rigor and reliability of data analysis. All statistical analyses will be performed using SAS or R software by professional statisticians

--	--

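### Omics biomarkers are selected and their change estimated in the same 50 patients with no correction for selection; under a Bonferroni-type cut-off over thousands of features, moderate changes that pass would be overstated about 1.4 to 2 times

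*Combined protocol and SAP*

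**What the plan says.** All references are to the combined protocol and SAP.

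- Study Design row: "Single-center, open-label, exploratory clinical study". Sample Size row: "50 ACS patients post-PCI in an open-label group". No derivation of the 50 is given.
- Objective row: one aim is to "explore key biomarkers".
- Evaluation Criteria row, multi-omics item: "Including platelet transcriptomics, metabolomics, proteomics, microbiomics". The number of features per layer is not stated. The platelet-function item is a short named list: two granule markers, then "surface activation markers (P-selectin/CD62P, GPIIb/IIIa complex/CD41/CD61), platelet-leukocyte aggregation (CD41 and CD15").
- Section 2.3 gives both sets primary status: "Evaluate treatment effects through multi-omics analysis and platelet function indicators". The tests are used "to compare pre- and post-treatment differences".
- Section 2.7 covers multivariable analyses and says to "use Bonferroni correction or Holm-Bonferroni method to adjust significance levels". It does not define the family of tests.

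The text does not say by what rule a feature becomes a key biomarker. It also does not say how the size of a selected feature's change will be estimated, beyond the comparison in 2.3.

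**The concern.** A multiplicity correction limits how many null features are declared positive. It does nothing to the size of the estimates that survive. With 50 patients and a cut-off spread over thousands of features, the smallest change that can pass is larger than a moderate true change. A moderate feature therefore passes only when chance has pushed its observed change above its true one, and the average reported change among those that pass is too large by construction.

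What is at stake is the set of effect sizes attached to the features named as key. Because 2.3 makes the omics results primary, those sizes are part of the main result. Nothing in the plan would tell a reader how much of each reported change is due to selection.

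**Working it through.** **Plan's own figure.** The only stated figure is 50 patients. It cannot be reproduced, because no alpha, power, effect size, SD or dropout rate is given.

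**Inputs from the documents.** n = 50 in one group; a before/after comparison, taken as a paired t-test with 49 df; Bonferroni or Holm.

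**Assumptions.** Two-sided alpha 0.05; m = 1,000 to 20,000 features in the family; selection by that cut-off; true change d = 0.4 to 0.5 in units of the SD of the within-patient change; normal data; all 50 evaluable. Holm's first step is Bonferroni, and its later steps (0.05/(m − k + 1)) are nearly the same while few of thousands of features pass.

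**Step 1: smallest change that can pass.** A feature passes if |t| = |mean change| / (s/√50) exceeds the critical value t_c at 0.05/m. The observed standardised change must therefore exceed t_c/√50, with √50 = 7.071.

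- m = 1,000: 4.447/7.071 = 0.629
- m = 5,000: 4.925/7.071 = 0.697
- m = 20,000: 5.327/7.071 = 0.753

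All three lie above a true change of 0.4 or 0.5.

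**Step 2: inflation among features that pass.** Raw inflation is E[mean change | |t| > t_c] / true mean change. Standardised inflation is E[mean change/s | |t| > t_c] / d. Both were integrated over the sampling distributions of the mean and of s.

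| m | true d | passes | raw | standardised |
|---|---|---|---|---|
| 1,000 | 0.4 | 7% | 1.62 | 1.76 |
| 1,000 | 0.5 | 21% | 1.36 | 1.45 |
| 1,000 | 0.6 | 43% | 1.19 | 1.25 |
| 5,000 | 0.4 | 3% | 1.72 | 1.92 |
| 5,000 | 0.5 | 11% | 1.43 | 1.56 |
| 20,000 | 0.4 | 1.5% | 1.80 | 2.05 |
| 20,000 | 0.5 | 6% | 1.50 | 1.66 |
| 20,000 | 0.6 | 18% | 1.31 | 1.41 |

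The standardised figure is higher because a feature also passes more easily when its observed SD happens to be small.

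**Step 3: check by normal approximation.** Inflation ≈ [μ + φ(c − μ)/(1 − Φ(c − μ))]/μ, with μ = d√50 and c the normal critical value. For m = 5,000 and d = 0.4: μ = 2.828, c = 4.417, φ(1.589) = 0.1129, 1 − Φ(1.589) = 0.0561. Then (2.828 + 0.1129/0.0561)/2.828 = (2.828 + 2.014)/2.828 = 1.71, against 1.72 in the table.

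**Step 4: sensitivity.**

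- Smaller true effect, d = 0.3: raw 2.07 to 2.31 for m = 1,000 to 20,000, with 1.8% down to 0.25% passing.
- Larger true effect, d = 0.8: raw 1.04 to 1.09, standardised 1.06 to 1.14.
- About five platelet-function markers as their own family (m = 5, an assumption): d = 0.4 gives 1.24 raw and 1.28 standardised; d = 0.5 gives 1.10 and 1.12.
- Unadjusted cut-off (m = 1): raw 1.13 at d = 0.4 and 1.04 at d = 0.5, with many more false positives.
- Only 40 evaluable patients, m = 10,000: d = 0.4 gives 1.92 raw and 2.28 standardised; d = 0.5 gives 1.60 and 1.84.

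**The case against.** The strongest objection is that the selection step is inferred. Section 2.7 ties the correction to multivariable analyses, defines no family, and does not say that biomarkers are chosen by it. Section 2.3 only says that changes are compared. If the change in every feature were reported without regard to significance, this bias would not arise in that full list. This stands, and it is why every figure here is conditional. It does not remove the point: naming some features as key requires some selection, the Bonferroni-type cut-off is the only one the plan offers, and no other rule is stated.

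The Objective row can also be read as seeking biomarkers of the disease, with the drug's effect in a separate clause. That is a fair reading. The calculation applies where key biomarkers are identified from the before/after change, which is the comparison that 2.3 specifies for the omics data.

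The exploratory label is a further defence. It lowers the severity, but it does not correct the estimates.

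Two stronger readings are tempting. A reader might infer that any moderate biomarker will be overstated 1.5 to 2 times. That is too broad: the bias affects only features that pass, the raw figure at 0.5 SD reaches 1.5 only at about 20,000 features, and it is lower at 0.6 SD and for the platelet markers. A reader might also infer that later trials will be sized on these effects and be too small. The documents describe no such later study.

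**Conclusion.** The concern holds in conditional form, as a low-severity improvement. The documents establish that discovery and estimation share the same 50 patients and that nothing in 2.1 to 2.8 corrects the size of selected effects. The amount rests on assumptions that the plan does not supply: alpha, feature count, true effect, and selection by the 2.7 cut-off. With two-sided 0.05 over 1,000 to 20,000 features, true changes of 0.4 to 0.5 SD that pass are overstated 1.36 to 1.80 times on the raw scale and 1.45 to 2.05 times when standardised. The companion problem is at least as large: roughly 79% to 98.5% of such features would not pass at all.

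**What to change.** 1. In 2.3 and 2.7, state the rule by which an omics feature is named a key biomarker, the family over which the correction runs (for example, each omics layer, with the platelet-function markers as a separate family), and the alpha. This must come first, because a bootstrap of the selection cannot be specified without it.
2. In 2.3, for each feature so named, report beside the raw change a selection-corrected estimate: either empirical-Bayes shrinkage within its omics layer, or a bootstrap over patients that re-runs the whole rule. Add the share of bootstrap samples in which the feature was selected.

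The cost is some analysis time and smaller reported effects. No extra patients, visits or assays are needed.

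### No criterion clearly keeps out patients who took Xuesaitong or another Panax notoginseng product before Visit 1, so some baselines may already be on-drug

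*Combined protocol and SAP*

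**What the plan says.** The design is "50 ACS patients post-PCI in an open-label group", with no control arm. The Medication Information section gives "Trial Drug: Xuesaitong Soft Capsule" and "Main Component: Panax Notoginseng Saponins".

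Inclusion (2) admits patients "Within 4 weeks post-PCI". The Study Procedure section sets "Visit 1 (-1D to 0D) and Visit 2 (4w ± 3d), with no follow-up period"; neither a run-in nor a washout is described.

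Three of the 13 exclusion criteria come near prior use:

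- (10), second sentence: "Participation in other clinical trials and taking trial drugs within the past 3 months".
- (12): allergy to a component of the product.
- (13): "Other conditions deemed inappropriate for participation by the investigator".

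On analysis, section 2.3 of the Statistical Analysis Plan compares values before and after treatment. Efficacy is analysed in two sets. The FAS (1.1) keeps everyone enrolled and dosed at least once. The PPS (1.2) keeps, among other conditions, those who "did not use concomitant medications affecting efficacy evaluation". The Evaluation Criteria list concomitant medications as an item to collect, without tying it to a visit or saying what follows from it.

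**The concern.** With one group, the before/after comparison is the only source of evidence about the product. It can reflect starting the product only in patients who were not already taking it at Visit 1. A patient given a notoginseng product after PCI and screened on day 20 could meet every written criterion. That patient would be measured on the active component at both visits and would contribute little or no drug-related change.

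A mean over such patients and new starters mixes two contrasts, continuing and starting. With no control arm, nothing else in the design would reveal the mixture. If prior use is not asked about at entry, analysts cannot fully recover it later.

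**Working it through.** **Step 1: does any criterion cover prior use?** There are two readings of exclusion (10).

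| Reading of (10) | Xuesaitong in ordinary care | Other Panax notoginseng product |
|---|---|---|
| Investigational drugs taken in other trials (most natural, since drug-taking is joined by *and* to trial participation) | not covered | not covered |
| *Trial drugs* means the product labelled as the trial drug, which is also how (12) uses the term | arguably covered | not covered |

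Criterion (12) concerns allergy only. Criterion (13) leaves the matter to the investigator and does not mention prior use. Inclusion (1) to (4) do not mention it either.

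**Step 2: can exposure occur before Visit 1?** Yes. Entry is allowed up to 4 weeks after PCI, Visit 1 is on day -1 to 0, and no drug-free interval is required.

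**Step 3: what does exposure do to the mean change?** Let D be the drug-related change in a new starter, R the change from post-PCI recovery and background therapy, and f the share already exposed with complete carry-over. Then

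mean observed change = R + (1 − f)D.

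Only D is diluted. If R and D have the same sign, the observed change shrinks. If they have opposite signs and R is the larger, the observed change grows in absolute size. R is unknown, so the direction for a given marker is not determined.

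**Step 4: illustrative size.** The documents give n = 50 but no alpha, power, effect size, SD or prior-use rate for it, so there is no stated figure to reproduce. The assumptions are a paired t-test, two-sided 5% without multiplicity adjustment, R = 0, complete carry-over in every exposed patient, and an effect set where 50 unexposed patients give 80% power.

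- That effect is d = 0.404 SD of the paired difference. The noncentrality is 0.404 × √50 = 2.858, against a critical t of 2.010 on 49 degrees of freedom.
- With a share f exposed, the standardised effect becomes d(1 − f) / √(1 + f(1 − f)d²). The denominator allows for the extra variance from mixing two kinds of patient.
- Example, f = 20%: 0.404 × 0.80 = 0.323; √(1 + 0.16 × 0.404²) = 1.013; 0.323 / 1.013 = 0.319; power 60%.

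| Assumed share f | Expected patients of 50 | Standardised effect | Power |
|---|---|---|---|
| 0% | 0 | 0.404 | 80% |
| 2% | 1 | 0.396 | 78% |
| 5% | 2.5 | 0.383 | 76% |
| 10% | 5 | 0.361 | 71% |
| 20% | 10 | 0.319 | 60% |
| 30% | 15 | 0.278 | 49% |

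The chance of enrolling at least one prior user among 50 is 1 − (1 − f)^50, which is 64%, 92% and 99% for f = 2%, 5% and 10%.

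**The case against.** Several counter-arguments have force.

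- **Exclusion (10) may already cover Xuesaitong.** The protocol itself labels Xuesaitong the trial drug. This stands as an ambiguity, so it would be too strong to say that the protocol plainly permits prior Xuesaitong. Other notoginseng products remain outside (10) on either reading.
- **There are safeguards.** An investigator could use (13). The PPS medication rule states no time limit, so it should not be read as confined to use during the study. A patient still taking another notoginseng product could be dropped from the PPS. This stands in part: (13) gives no guidance, the PPS rule names no drugs and no period before Visit 1, and the FAS has no such rule.
- **The direction is not fixed.** A reader might infer that every omics and platelet change is pulled toward zero, or that a drug-free Visit 1 would by itself make the contrast a valid measure of drug effect. The documents support neither. Conventional treatment and recovery contribute to the change in everyone, exposed or not.
- **The size is assumed.** A reader might take the power losses as findings. They depend on an exposed share the documents do not give, and at 2% or 5% they are small. Section 2.7 plans Bonferroni or Holm correction for multivariable analyses, so 80% at an unadjusted 5% is a convenient starting point and not the trial's actual power.
- **The study is exploratory.** This limits how serious the gap is. It does not remove it, because the stated objective includes the biological basis of this product's action, which an on-drug baseline blurs.

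**Conclusion.** The gap is real but narrower than it may look. As written, the plan can admit patients whose Visit 1 is already on Xuesaitong or, more clearly, on another Panax notoginseng product, and the FAS then keeps them. In those patients the drug-related part of the change is diluted; the effect on the total change cannot be stated from the documents.

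Under the assumptions shown, power falls from 80% to between 78% and 49% as the exposed share runs from 2% to 30%. The loss would be smaller if carry-over were partial, and there would be none if no prior users were enrolled. The point should be acted on because the repair is cheap and later analysis cannot fully replace it, not because the damage has been shown to be large.

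**What to change.** 1. Reword exclusion (10) so that it says which drugs it means, or add one exclusion criterion for use of Xuesaitong or any other Panax notoginseng preparation within an interval before Visit 1. The sponsor should set and justify the interval. Nobody should be asked to stop a product in order to qualify.
2. Record prior use at Visit 1 with a specific screening question. The concomitant-medication item cannot be relied on for this, because it is not tied to a visit and need not capture a product already stopped.
3. For patients already enrolled, prespecify a sensitivity analysis of the before/after change that leaves out those with prior exposure. Keep the FAS and PPS analyses as planned. Moving the primary analysis to unexposed patients would be out of proportion to a problem of unknown frequency.

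The cost is one eligibility line and one question, with no extra visit or assay. Recruitment may be slightly slower, and the history of products stopped before Visit 1 will be incomplete for some patients.

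### Does requiring complete but undefined main-outcome data for the per-protocol set throw away valid assay pairs?

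*Combined protocol and SAP*

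**What the plan says.** Section 1.2 defines a single PPS at the level of the participant. Besides eligibility, completion, 80–120% compliance and no interfering medication, it asks that the participant "had complete main outcome data, and no major protocol violations". The plan does not define the main outcome, does not say what makes it complete, and gives no rule for a failed assay.

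The nearest definition is in section 2.3: "Primary Efficacy Indicators: Evaluate treatment effects through multi-omics analysis and platelet function indicators". The methods listed there are used "to compare pre- and post-treatment differences", so a usable observation is a Visit 1/Visit 2 pair. The Evaluation Criteria describe the multi-omics work as "Including platelet transcriptomics, metabolomics, proteomics, microbiomics", which is four layers. Platelet function comprises granule markers plus "surface activation markers (P-selectin/CD62P, GPIIb/IIIa complex/CD41/CD61), platelet-leukocyte aggregation (CD41 and CD15"), which makes three marker groups.

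The FAS in section 1.1 is "Defined according to the ITT principle, including all enrolled participants who received at least one treatment", with no condition on outcome data. Section 1.3 adds: "Efficacy indicators will be analyzed for both FAS and PPS". The design is "Single-center, open-label, exploratory clinical study" with 50 patients in one group.

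**The concern.** A completeness condition is easy to apply when there is one primary variable. Here the primary domain spans several laboratory platforms, and there is one PPS for all of them. If the main outcome means everything that 2.3 calls primary, a patient whose microbiome sample fails at Visit 2 also leaves the PPS analyses of platelet markers, proteomics and the rest, although those pairs were measured. With seven blocks, one failure discards six valid pairs.

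Two things would be at stake. The PPS would be thinned by laboratory failures that have nothing to do with adherence, which most of its other conditions address, and its estimates would lose precision. Also, two statisticians could build different PPS populations from the same data, because the text does not choose between an all-components reading and an endpoint-by-endpoint one.

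**Working it through.** The documents state no alpha, power, SD, dropout or assay failure rate, so there is no figure of the plan's own to reproduce. The check is how large the loss could be, and under which assumptions.

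**Inputs**
- N = 50 (Sample Size).
- k = number of blocks that must all be usable. Three readings: k = 2 (the components named in 2.3), k = 5 (four omics layers plus platelet function as one), k = 7 (four layers plus three marker groups).
- q = probability that one block's pre/post pair is usable. Assumed: 0.99, 0.98, 0.95, 0.90.
- All other reasons for leaving the PPS are set to zero.

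**Formulas**
- Completeness judged by endpoint: n = 50q.
- All blocks required, independent losses: n = 50q^k.
- All blocks required, half of each block's loss shared: s = 1 − 0.5(1 − q), n = 50·s·(q/s)^k.
- All blocks required, losses fully shared: n = 50q.
- Ratio of standard errors of a mean paired change: √(50q / n).

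**Expected PPS size, independent losses**

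| q | by endpoint | k = 2 | k = 5 | k = 7 |
|---|---|---|---|---|
| 0.99 | 49.5 | 49.0 | 47.5 | 46.6 |
| 0.98 | 49.0 | 48.0 | 45.2 | 43.4 |
| 0.95 | 47.5 | 45.1 | 38.7 | 34.9 |
| 0.90 | 45.0 | 40.5 | 29.5 | 23.9 |

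**At q = 0.95**
- Independent: 50 × 0.95² = 45.1, 50 × 0.95⁵ = 38.7, 50 × 0.95⁷ = 34.9. Extra loss against 47.5: 2.4, 8.8 and 12.6 patients. SE ratios: √(47.5/45.1) = 1.03, √(47.5/38.7) = 1.11, √(47.5/34.9) = 1.17.
- Half shared: s = 0.975 and q/s = 0.9744, giving 46.3 (k = 2), 42.8 (k = 5) and 40.6 (k = 7). The SE ratio for k = 7 is √(47.5/40.6) = 1.08.
- Fully shared: 47.5 for any k, with no extra loss.
- Unadjusted 95% CI half-width, t(0.975, n − 1)/√n, in SDs of the change: 0.29 at n = 47.5, 0.32 at 40.6 and 0.34 at 34.9.

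Across the whole table the extra loss runs from 0.5 patients (q = 0.99, k = 2) to 21.1 (q = 0.90, k = 7). It is zero under shared losses or an endpoint-by-endpoint reading.

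**Which q is relevant.** Section 1.2 separately requires completion of treatment and follow-up, so patients who miss Visit 2 plausibly leave the PPS on that ground already. What remains in 1 − q is then sample or assay failure alone, block by block. Nothing in the documents favours 5% over 1%. At 1%, even k = 7 costs 49.5 − 46.6 = 2.9 patients, an SE ratio of 1.03.

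**What happens in the FAS.** Section 1.1 sets no completeness condition, and 1.3 analyses efficacy there too. A paired comparison in the FAS uses every measured pair for that endpoint, an expected 50q, whatever happened to the other blocks. The PPS wording cannot reduce that number.

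**The case for a change.** The strongest reply is that the ambiguity is real and cheap to remove. Section 1.3 does not rank the FAS above the PPS, so a PPS shrunk by laboratory failures would be reported beside the FAS as an equal. Section 2.1 mentions only the PPS and safety set when it speaks of determining analysis sets. The plan does not say when PPS membership is fixed, so the reading could be chosen after assay results are known. With seven blocks and 90% usable pairs, the strict reading would keep fewer than half the patients.

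Part of this stands. The term is undefined, the arithmetic is right under its assumptions, and there is some room for discretion. The rest carries less weight. The omission in 2.1 looks clerical, since 1.1 defines the FAS and 1.3 assigns efficacy to it. The seven-block case needs an unstated reading, the finest possible count of blocks, a high failure rate and independence, all at once.

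Judging completeness by endpoint is not clearly better either. For an omics layer with many features, the endpoint itself would need defining, or membership could change feature by feature, and each table would describe different patients. In a study that aims to relate several omics layers to one another, a common complete-case set beside an unrestricted FAS is a defensible pairing. That the change costs one line does not show that the plan is defective.

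**Conclusion.** The concern does not call for a change. Section 1.2 leaves a definition open, but a requirement for primary-outcome data is conventional for a PPS, and analysts can settle its scope by assay layer, on sample and quality-control status, without altering the design or any data collected.

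The possible cost is lost precision in one of two analysis sets. At an assumed 95% usable pairs and independent losses, it is 2.4 patients (SE about 3% larger) with the two components the plan names, rising to 12.6 patients (SE about 17% larger) with seven blocks. It is nil if failures coincide or completeness is judged by endpoint. These figures rest on an assumed failure rate, block count and correlation, none of which the documents give.

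The FAS keeps every measured pair, although the plan states no missing-data rule for it. The study is single-arm and exploratory, so no confirmatory test depends on the PPS, and what can be concluded from the FAS does not depend on how this phrase is read.
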